- Group 2: Joint Line Landmark Based (sham Ultrasound)
- Group 3: Suprapatellar Ultrasound Guided
- Group 4: Suprapatellar Landmark Based (sham Ultrasound)

The patients will be blinded to their group assignment prior to the first injection and will not be able to see which technique is employed. The provider performing the injections will not be blinded. The third injection (only) will be different in that contrast medium will be injected along with the hyaluronan. Following the third injection, fluoroscopy will be used to determine presence/absence of the contrast medium into the joint. The radiologist interpreting these images will be blinded to the technique employed. At 3 months following the third injection, the patients will be contacted by a surveyor blinded to the group assignment.

Objectives and Specific Aims

- 1. To compare the accuracy of injections into the knee joint with two different approaches, joint line and suprapatellar pouch
- 2. To determine if the addition of ultrasound guidance to traditional landmark-based techniques enhances the accuracy of these techniques
- 3. To examine differences in patient perceived pain and functioning of their knee joint following the injection series.

Medical Application

Injections into the knee joint are an exceedingly common procedure by a variety of specialists, primary care physicians, and non-physician clinicians. Knowledge of the most accurate and clinically effective injection technique will positively impact countless future patients. If we find that the addition of ultrasound guidance increases accuracy, as

we hypothesize, patient-oriented results should be better with fewer complications. This will allow the patient to return to activity quicker.

Background and Significance

Literature Review (as of 18 November 2010) and Preliminary Data and/or Findings.

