- **a.** There will be a Research Coordinator at the trial site who will administer the consent and HIPAA authorizations. This will be performed with a standardized consent form (Appendix A), including a scripted discussion of the study procedures and a scripted discussion of risks inherent in the injection techniques
- **b.** Upon completion of consent, the Coordinator will have the subject explain their understanding of the concept of treatment in their own words to ensure the subjects understand the consent.

Study Design

The study will be a randomized, double-blinded clinical study comparing four techniques for intra-articular knee injections.

The study investigators will receive a list of 120 computer generated random numbers from

Page 8 of 17 Version 2.0 one to four. No more than 30 will be in each group to ensure that each group is the correct size. Upon entry into the study, and prior to the first injection, subjects will randomized by selecting a sealed envelope from a box containing an equal number of envelopes for each of the four treatments groups. The envelope will be given, unopened, to the study doctor. The subject will be blinded to their study group assignment.

Double-blinding will be done as follows: The subjects will be blinded to whether ultrasound was used to guide their treatment. The radiologist, who will review the fluoroscopic images after the injections, will be blinded to treatment group assignment. The injecting physician will not be blinded to the treatment group assignment. Treating physicians (injecting physicians) will perform the technique as detailed below based on the assignment of the participant. Subjects and the radiologists will both be asked to guess their treatment group at each point in the data collection to determine the effectiveness of the blinding process. The Surveyor will also be blinded to the treatment group allocation.

The injecting physicians will consist of orthopedic surgeons, sports medicine fellows, or sports medicine fellowship trained primary care physicians. All injecting physicians will receive a minimum of 2 hours of hands-on training specific to the procedures employed in this study. Additionally, they will be supervised for their first several ultrasound-guided procedures to assure competence with the techniques.

Study Methodology/Procedures

Appointment 1

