The Joint Line Ultrasound (JLUS) group will receive a standard medial or lateral joint line injection aided by ultrasound guidance. Specifically, this technique will entail palpation by the clinician of the soft tissue triangle formed by the tibial plateau, border of the patellar tendon, and the distal femoral condyle as found on both the medial and lateral joint line with the patient sitting on the edge of an examination table. Their knees will be bent to 90 degrees of flexion. The decision between a medial versus a lateral approach will be made by the provider performing the injection and based on the patient's anatomy and the provider's determination of the most facile side in which to perform the injection, as is the traditional practice of performing this technique. The triangle felt to be most prominent (i.e. largest joint space) will be chosen as the injection site. The area will be prepped in the usual sterile fashion.

The injection will be performed as detailed above with real time ultrasound guidance. To accomplish this a 10 MHz linear array transducer from a standardized ultrasound unit (Logiq E ®, General Electric Healthcare, Chalfont St. Giles, United Kingdom) will be placed in an oblique orientation on the opposite soft tissue triangle from the intended injection site so that

the inner aspect of the opposite femoral condyle is visualized, but the ultrasound display will be positioned so that the patient cannot visualize the screen. The injection will occur through the soft tissue triangle and directed at a 45 degree angle to the inner aspect of the opposite femoral condyle, with the needle being advanced parallel to (in the longitudinal axis of) the US probe. When the needle is visualized to be adjacent to the articular cartilage, a small bolus of saline will be injected. When the provider is satisfied that the needle tip is underneath the synovium overlying the condyle, as evidence by the saline easily dispersing underneath the synovium and not accumulating adjacent to it, the viscosupplement will be injected followed by the contrast.

Group 2: Joint Line Landmark (JLL)

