The same determination of medial versus lateral approach as described in Group 1 will be made. The injection will be performed as described above. The ultrasound probe will be placed in an oblique orientation on the opposite soft tissue triangle from the intended injection site, but the ultrasound display will be positioned so that the patient cannot visualize presence or absence of the needle, and the image will be placed on "FREEZE" so that no active images are being viewed. The injection will be completed based strictly on tactile feedback from the injecting physician. The needle will enter the predetermined soft tissue triangle and directed toward the joint space. Once the injecting physician believes that the needle is positioned within the joint space, the viscosupplement will be injected followed by the contrast.

Group 3: Suprapatellar Ultrasound Guided (SPUS)

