Real time ultrasound guidance using a standardized ultrasound unit with a 10 MHz linear array transducer (Logiq E ®, General Electric Healthcare, Chalfont St. Giles, United Kingdom) will be used to guide the injection for this group. The ultrasound display will be positioned so that the patient cannot visualize the screen. After sterile prep of the anteriolateral suprapatellar area (approximately 1 cm superior to the patella at a level approximating that of the lateral patellofemoral joint space), the suprapatellar pouch will be visualized. First, a longitudinal view capturing the proximal patella and the plane between the prefemoral fat pad (superficial to the femur) and suprapatellar fat pad (deep to the quadriceps tendon) will be obtained. Presence or absence of an effusion, visualized as a localized collection of anechoic material within this plane, will be noted. Next, the probe will be turned 90 degrees to a transverse view of the plane just proximal to the patella. Small adjustments in probe positioning will be done to create the best visualization of the suprapatellar pouch. After the desired visualization is achieved the needle will be inserted just lateral to the vastus lateralis in the longitudinal axis of the US probe and angled medially until the tip of the needle is within the suprapatellar pouch. Should an effusion be present, this will serve as the target landmark. In this instance, the effusion will be aspirated using a clean 5ml syringe prior to the injection. In the absence of an effusion, the target landmark will be the plane between the prefemoral and suprapatellar fat pads. In the absence of an effusion, injection of saline will be done first to dissect this plane further to assure that the needle tip is within the suprapatellar pouch. Once the injecting physician is confident of needle position with the pouch, the viscosupplement will be injected followed by the

contrast.

Group 4: Suprapatellar Landmark (SPL)

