Patients randomized to the Suprapatellar Landmark (SPL) group will receive the same procedure as the Suprapatellar Ultrasound Guided (SPUS) group., with the exception of the sham ultrasound. To accomplish this, the ultrasound probe will purposely be positioned in the transverse plane of the suprapatellar area but the ultrasound display will be positioned so that the patient cannot visualize the screen, and the "FREEZE" button will be activated so that no active image is transmitted. The display will be positioned such that visualization by the patient will not be possible. The injecting physician will insert the needle lateral to the vastus lateralis toward the suprapatellar pouch. When the injecting physician believes the needle tip is in the pouch, the viscosupplement will be injected followed by the contrast.

It should be noted, that none of the participants in the study will be given the ability to visualize the ultrasound screen or injection procedure.

- 5. Following each injection, all patients will conclude their encounter with the injecting physician by being asked to rate on a scale of 0 to 10 their procedural pain from the procedure. For pain, a score of 0 will correspond to no pain and 10 will correspond to the worst pain they have ever experienced. After each injection, and at the three month follow up telephone call, the subjects will be asked to rate their overall procedure satisfaction on a 0-10 scale where "0" represents complete dissatisfaction and "10" represents complete satisfaction.
- 6. After the third injection, and after answering these questions, the patient will proceed directly to the Radiology Department.
- 7. Images of the joint will be obtained following the third injection. These images will be analyzed by a radiologist blinded to the technique employed and used to determine presence of or absence of the contrast medium within the joint.

Appointment 4 (telephone)

8. Subjects will be contacted approximately three months after the procedure by a Surveyor and the WOMAC Osteoarthritis Index will be repeated. The patients will be asked to rate their procedural satisfaction and also detail other therapies they have employed since the injection. This will include supplements, exercise (frequency and duration), acupuncture, physical therapy, etc.

Data Collection

Data collection will occur at three points during the investigation:

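### Patients are described as blind to their group, but the masking can hide only whether ultrasound guidance is live, not whether the injection is at the joint line or above the patella

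*Combined protocol and SAP*

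**What the plan says.** The Research Design section labels the trial a double-blind randomised trial of four groups, each defined by an approach and by live or sham ultrasound. Methodology/Technical Approach says that patients are blinded to group and "will not be able to see which technique is employed". Study Design repeats the broad claim, "The subject will be blinded to their study group assignment", and then, in explaining how blinding is achieved, makes a narrower one: "The subjects will be blinded to whether ultrasound was used to guide their treatment".

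The masking is a screen turned away, a sham probe with a frozen image, and a general statement after the Group 4 description that "none of the participants in the study will be given the ability to visualize the ultrasound screen or injection procedure". The documents do not say how the view of the procedure is blocked.

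The sites differ by approach. Joint line patients are treated "with the patient sitting on the edge of an examination table" with the knees at 90 degrees, and in the Group 2 text "The needle will enter the predetermined soft tissue triangle" beside the patellar tendon. Suprapatellar patients are prepared "approximately 1 cm superior to the patella" and injected lateral to the vastus lateralis. No patient position is stated for the suprapatellar groups. A bandage is applied at the end.

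To assess the blind, "Subjects and the radiologists will both be asked to guess their treatment group at each point in the data collection". No analysis or chance level is given.

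Under Statistical Consideration the primary endpoints are contrast in the joint, WOMAC and satisfaction. Data Analysis specifies one-way ANOVA with Tukey comparisons of all pairs for WOMAC.

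**The concern.** A sham that stays at its own approach's site can conceal only one of the two factors that define a group. Touch is not masked, the injection is given three times, and consent includes a scripted account of the study procedures, so a patient may be able to link the place of injection to an approach.

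Two things are at stake. First, WOMAC and satisfaction are scored by the patient, so a blinded telephone surveyor does not restore blinding. Aim 3 differences between approaches would be reported as double-blind when the patient's blinding to approach is not credible. Second, a guess of group mixes a factor that patients can probably identify with one that they should not. Read as a single score, it could discredit the guidance comparison that the sham was built to protect.

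**Working it through.** **The plan's own figure.** The documents give no number for blinding. The nearest figure is the WOMAC power statement (25 per group, effect size 0.809, two-sided 5%). The noncentral t calculation gives 80.0%, which agrees with the stated 80%. Nothing below changes it.

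**What each measure can hide.**

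| Measure | Guidance | Approach |
|---|---|---|
| Screen turned away | yes | no |
| Probe in place, image frozen | yes | no: the probe stays at its own approach's site |
| View of the procedure blocked (means not described) | helps | hides sight during the injection, not touch |
| Bandage | neutral | may show the site afterwards |

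**WOMAC pairs affected.** Four groups give 4 × 3 / 2 = 6 pairs. Those that cross approaches are 1v3, 1v4, 2v3 and 2v4, which is 4 of 6. The within-approach pairs are 1v2 and 3v4.

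**The guess of group.** Inputs: N = 120 (Study Design). Assumptions: a share *a* of patients recognise their approach, the others guess evenly among four groups, nobody can tell live from sham, and each patient contributes one guess. Then

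expected proportion correct = *a* × 0.50 + (1 − *a*) × 0.25.

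Suppose the pooled guess were tested against 25% with an exact one-sided 2.5% binomial test. The smallest count that rejects is 41 of 120 (34.2%), with P(X ≥ 41 | 0.25) = 0.0155.

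| Share recognising approach | Expected correct | Count of 120 | Probability of a flag |
|---|---|---|---|
| 0% | 25.0% | 30 | 1.6% |
| 25% | 31.3% | 37.5 | 27% |
| 50% | 37.5% | 45 | 80% |
| 75% | 43.8% | 52.5 | 99% |
| 100% | 50.0% | 60 | 99.98% |

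In every row the guidance blind is intact by assumption. The flag comes only from recognition of approach. If the guess is scored for guidance alone, within approach, the chance level is 50% whatever the value of *a*.

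**What an expectation effect could do (illustration only).** The documents give no size for such a bias. Assume a bias of *b* standard deviations between two groups of 30 and no true difference. With SE = √(2/30) = 0.258, the false-positive rate of one unadjusted two-sided 5% comparison is Φ(*b*/SE − 1.96) + Φ(−*b*/SE − 1.96). That is 12% at *b* = 0.2, 21% at 0.3 and 49% at 0.5. Under Tukey adjustment the rate for a given pair would be lower.

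**The case against.** The best defence has four parts.

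- **Sight.** A reader might infer that patients can watch where the needle goes. The documents say otherwise: neither the screen nor the procedure is visible to them. This stands. The point rests on touch, and on the bandage afterwards.
- **The guess.** A reader might infer that the blinding check is bound to mislead. The plan states no pooled score, no 25% benchmark and no test, and a four-group guess can be collapsed to live or sham within approach. This also stands: the check misleads only if it is pooled and judged against 25%. At 25% recognition a flag would be raised only about 27% of the time.
- **Bias.** A reader might infer that the cross-approach results are biased. Recognising the site is a risk, not a demonstrated effect. The protocol says that none of the approaches has been shown to be best, and the consent script is not available to show what patients are led to expect.
- **Wording.** The Methodology/Technical Approach sentence can be read as concealment before the first injection only. That reading does not rescue the claim, because Study Design repeats blinding to group without the limit.

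The opposite inference, that 1v2 and 3v4 are securely blinded, is not supported either. Group 1 receives a small saline bolus that the Group 2 text does not describe. Group 3 involves turning and adjusting the probe, whereas the Group 4 probe is placed in the transverse plane with a frozen image. The injecting physician, who is not blinded, also records satisfaction after each injection.

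**Conclusion.** Wrong as written. Blinding of patients to the four-level group is claimed, but the described masking can deliver at most blinding to guidance. The consequence is confined to patient-rated comparisons between approaches: four of the six WOMAC Tukey pairs, and any cross-approach statement about satisfaction. The pair count applies to WOMAC only, because no pairwise test is specified for satisfaction. The size and direction of any bias are unknown. Contrast in the joint, read by a blinded radiologist, is not affected, so the accuracy aims (1 and 2) stand.

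The guess check is a conditional problem. The range of 27% to 99.98% rests on the assumed 25% benchmark, a one-sided 2.5% test, N = 120, and recognition of approach by 25% to 100% of patients.

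**What to change.** 1. Reconcile Research Design, Methodology/Technical Approach and Study Design so that all say subjects are intended to be blind to guidance (live or sham) only, and not to approach. State how the view of the procedure is blocked.
2. Replace the subjects' guess of group with two questions: guidance (live / sham / don't know) and approach (joint line / suprapatellar / don't know). Keeping the second question shows how far approach was recognised. Evaluate the guidance guess within each approach against 50% among those who commit to an answer, and report the don't-know share.
3. In Data Analysis, state that cross-approach comparisons of WOMAC and satisfaction will be reported as not patient-blind. Describe 1v2 and 3v4 as intended to be blinded, subject to the check in item 2 and to the differences in the described procedures.

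The cost is protocol wording and one extra question. Sample size, visits and procedures do not change. The downside is a weaker double-blind claim for approach in Aim 3. The guidance check within each approach also rests on at most 30 + 30 = 60 patients.
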